B. Study Type and Design: This study is a longitudinal, repeated measures, double-blinded design with subjects randomly assigned to placebo, low (20 mg/d) or high (80 mg/d) atorvastatin therapy during a 12-week aerobic exercise training protocol. We expect to screen approximately 150 participants to enroll (randomize) a maximum of 80 participants. The overall goal is to have 60 participants complete all study procedures (20 in each group). Repeated measures design allows each subject to serve as their own control. Placebo groups are included to account for potential changes in muscle mitochondrial function independent of statin therapy over the 1 year dose-response.

C. Sample size, statistical methods, and power calculation: The randomization for study drugs will be carried out by the biostatistician using a computer-based random number generator at a 1:1:1 allocation. Sample size for the study is powered on the basis of detecting a difference in VO₂peak between the EX+Plac group and the EX+Atorva80 group as well as between the EX+Atorva20 group and the EX+Atorva80 group at 12 weeks post-treatment. In our previously published study(13) (Table 2) the EX only group had a mean 2.6 ml/kg/min increase in VO₂peak following 12 weeks of training while the EX+Statin group only had a 0.4 ml/kg/min increase in VO₂peak. The estimated effect size of between group differences is 0.9 (Cohen's d). The increase of VO₂peak in the EX+Atorva20 group is expected

to be similar to that of EX+Plac group. A sample size of 35 per group provides 80% of power of detecting an effect size of 0.75 for a two-sided, two-sample t-test at 0.025 levels. Here, we use 0.025 for each group comparison to maintain the overall type I error rate at 0.05 level using Bonferroni correction. Assuming variances similar to what was observed in the pilot study, this study is powered to detect a difference of 1.53 ml/kg/min VO₂peak between groups. These power calculations led to a desired final sample size of 105 (35/group). We plan an enrollment of 120 (40/group) subjects to account for 10% dropout rate. The subject enrollment will be split equally between the two sites. As an exploratory analysis, the mean difference of VO₂peak (EX+ Atorva20- EX+ placebo) and its 95% confidence interval (CI) will be estimated. If the lower bound of the 95% confidence interval is greater than -0.8 ml/kg/min, EX+ Atorva20 will be considered non-inferior to EX+ placebo.

D. Subject Criteria

[figure not shown]

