- Telephone screen: A telephone screen will be used to collect health history, concurrent medications, and physical activity level of potential participants prior to in-person screening.

- ii. Blood draw: A screening blood draw will be used to determine presence of genetic markers associated with increased risk of myopathy from statin, creatine kinase (CK), kidney function (GFR) and liver enzymes (ALT). CK, GFR and ALT will be used to detect abnormal muscle, kidney or liver function prior to enrollment. A blood draw will be repeated at 1 month to measure for myopathy, and changes in liver and kidney function from statin use.
- iii. Intravenous glucose tolerance test (IVGTT): The subject will arrive following an overnight fast (10-12 hrs). Upon arrival, anthropometrics and vital signs will be measured. A catheter will be placed in one arm for blood draws. A fasting blood draw (~14-16mls) will be used to determine blood glucose, insulin, total cholesterol, HDL-C, LDL-C, triglycerides. Creatine kinase (CK) and liver enzymes (ALT) will be tested at 6 and 12 months during IVGTT.. CK and ALT will be used to detect abnormal myopathy, and changes in liver function from statin use for participant safety. Following the baseline draw glucose (50%) will be injected at a dose of 0.3 g/kg. Insulin will be mixed with the participant's blood for injection. Blood (5ml) and insulin (1.25 ml) will be injected into a 250 ml bag of sterile saline and mixed thoroughly. A dose of 0.025 U/kg body mass will be administered at minute 20. These mixing procedures have been safely preformed at the CTSU for a recent study (INFORM; HSC#13453).. Serial blood samples (25 total) will be obtained from the other arm at minutes 2, 3, 4, 5, 6, 8, 10, 12, 14, 16, 19, 22, 25, 30, 40, 50, 60, 70, 80, 90, 100, 120, 140, 160, and 180. Plasma will be frozen at - 80°C for later determination of glucose and insulin, and insulin sensitivity will be calculated using a minimal model program (77). A total of approximately 622 ml of blood will be collect over the 12 month intervention. After analysis for current project is complete any remaining blood samples will be stored indefinitely for future research. Fasting blood draw will be repeated at , 4 and 12 weeks. The IVGTT will be repeated at week12.

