- a. Key personnel:** [name], [name], [name], [name], study physician at KUMC and [name], study physician at ECU.
- b. Plan for safety monitoring and review:** [name] will serve as the Chair of the Data Safety Monitoring Board and will convene every 6 months with the other members, Drs. [name] and [name] to make decisions on safety of the participants. Enrollment data will also be reviewed twice a year by the DSMB. In addition, data will be reviewed on a yearly basis with the biostatistician, [name] to determine if the studies should be shortened due to either no measured effect or due to effects that are greater than what power calculations indicated. If problems occur with participants, blinded study staff will alert [name]. [name] will have access to dose and type of statin and will consult the study physicians cardiologist to make a decision on whether the subject should be removed from the study for safety concerns. The PI and other key personnel will be examining research data on a subject to subject basis to ensure it is accurate and to address any potential problems that may arise with the protocols. In addition, Drs. [name] and [name] will discuss data at least once per month through in person meetings or by phone to ensure that data collection is occurring in a consistent manner at both locations.**Plan for adverse event reporting:** Adverse events will be defined as any untoward medical occurrence in study participants or others immediately involved in the performance of the protocol, which does not necessarily have a causal relationship with the study treatment, but results in a change in intervention, daily function, hospitalization or rated category 3 or above using the National Cancer Institute Common Terminology Criteria for Adverse Events (CTCAE) v3.0. Expected events such as slight muscle soreness consistent with statin therapy, or those consistent with a participant's prior medical history not sufficient to alter the intervention will not be considered an AE. Staff involved in performance of the protocol (e.g. coordinators) will continually monitor participants for adverse events throughout the intervention, and study staff will assess adverse events at every testing visit as well as during regularly scheduled telephone assessments with all randomized participants.

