- E. Quality Assurance / Monitoring:** Data will be reviewed twice a year by the Board Chair. In addition, data will be reviewed on a yearly basis with the biostatistician, [name] to determine if the studies should be shortened due to either no measured effect or due to effects that are greater than what power calculations indicated. The PI and other key personnel will be examining research data on a subject to subject basis to ensure it is accurate and to address any potential problems that may arise with the protocols. In addition, Drs. [name] and [name] will discuss data at least once per month through in person meetings or by phone to ensure that data collection is occurring in a consistent manner at both locations.

V. Data Analysis and Reporting

- A. Statistical and Data Analysis:** This project is a two-factor study. One factor is treatment group (between subjects) and a second factor is time of data collection (0, 1, 6, and 12 months) (within subject). The data analysis will be carried out for the primary outcome variable of cardiorespiratory fitness, in addition to other outcome variables (muscle mitochondrial change, and insulin sensitivity, etc.). For each measure, its baseline measure and age will be added as covariates to adjust for the individual difference at baseline. Two-way interaction between treatment and time will be added in the model for testing if the outcome changes differently between groups over time. Additional variables, such as demographics, BMI, physical activity, etc. may also be included as covariates. If the test of trend difference is significant, then the comparison at each time point will also be considered to identify when the difference between groups reaches the maximum. Least Square Means will be used for the aforementioned comparisons. The statistical analysis will be performed with mixed procedure in STATA 13.1 (StataCorp LP, College Station, TX). Mixed model does

not require complete data for a longitudinal study. Residual analyses will be conducted and efforts to address those will be made, including appropriate transformations.

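### Yearly reviews may shorten the trial for a large or absent effect under no written rule, so the stated 5% overall error and 80% power are not ensured

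*Combined protocol and SAP*

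**What the plan says.** Section IV.E has the data reviewed yearly with the biostatistician to judge whether the "studies should be shortened due to either no measured effect or due to effects that are greater than what power calculations indicated". Section II.K.b contains the same provision ("to determine if the studies should be shortened due to either no measured effect"). Section IV.A adds an unblinding after 1 year, partly so that a named person can see whether outcome effects are proving more or less significant.

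Section II.C sets the error rate: "Here, we use 0.025 for each group comparison to maintain the overall type I error rate at 0.05 level using Bonferroni correction". The two comparisons are placebo versus 80 mg and 20 mg versus 80 mg. On power it states: "A sample size of 35 per group provides 80% of power of detecting an effect size of 0.75", for a two-sided two-sample t-test. It also reports, from the previous study, "The estimated effect size of between group differences is 0.9".

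Section V.A describes a mixed model with baseline and age as covariates and a treatment-by-time interaction. It does not mention interim analysis. The half-yearly DSMB review in II.K.b concerns safety and enrolment and supplies no efficacy rule.

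**The concern.** A review that can shorten the trial because the effect looks large is an interim efficacy analysis, whatever it is called. The Bonferroni split in II.C uses the whole 0.05 on two comparisons at one analysis and leaves nothing for earlier looks. The 80% power likewise assumes that every trial runs to 35 per group.

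The trigger is undefined in several ways. The powered effect is d = 0.75 but the expected one is 0.9. Nothing says whether one comparison suffices or both must qualify, whether direction counts, whether significance is also needed, or whether the no-effect limb binds. A large observed effect is also not the same as a significant one early on, and stopping on a large early estimate exaggerates the effect. A rule written after by-arm data have been seen could not restore error control.

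**Working it through.** **Inputs from II.C.** Two-sided 0.025 per comparison, 35 per group, d = 0.75, 80% power, 1:1:1 allocation, 80 mg arm shared by both comparisons.

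**The plan's own figure.** The exact two-sample t-test at two-sided 0.025 with d = 0.75 needs 35.08 per group; power at 35 is 79.9%. Error over two comparisons is at most 0.025 + 0.025 = 0.05. Both figures reproduce for a single final analysis.

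**When is a large d significant?** With n per group, p < 0.025 requires |d| > t(0.9875; 2n − 2) × √(2/n).
- n = 12: 2.405 × 0.408 = 0.98
- n = 18: 2.345 × 0.333 = 0.78
- n = 35: 2.292 × 0.239 = 0.55

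At 12 or 18 per group an observed d just above 0.75 is therefore not yet significant. If the true d is 0.75, 40% of d > 0.75 triggers at 12 per group and 7% at 18 per group are not significant. The mean observed d at such a trigger is 1.12 and 1.05, that is 1.12/0.75 = 1.49 and 1.05/0.75 = 1.40 times the truth.

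**Error and power under candidate rules.** Assumptions, none of them in the protocol: one, two or three roughly equally spaced interim looks (at 18; 12 and 23; 9, 18 and 26 per group); normal data; unadjusted pairwise t-tests; each comparison tested at 0.025 wherever the trial stops. There were 200,000 simulated trials per scenario, with simulation error of about 0.06 percentage points near 8%. Error is family-wise under no difference. Power is for placebo versus 80 mg when both true effects are 0.75. Entries are for one / two / three looks.

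| Stopping rule | Error, % | Power, % |
|---|---|---|
| No interim look | 4.6 | 80 |
| Either \|d\| > 0.75, any direction | 7.7 / 7.8 / 8.1 | 67 / 50 / 39 |
| Either d > 0.75, 80 mg worse only | 6.2 / 6.2 / 6.4 | 67 / 50 / 39 |
| As above, plus binding stop if both d ≤ 0 | 4.3 / 4.1 / 4.1 | 67 / 50 / 39 |
| Both \|d\| > 0.75 and both p < 0.025 | 4.8 / 4.9 / 5.1 | 81 / 81 / 81 |

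At 20 per group (the completer target in II.B), the two-sided either-comparison trigger gives 6.1 to 6.3% and the directional one 5.3 to 5.4%.

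Power falls for two reasons: the trigger can fire before significance, and it can fire on the other comparison. Requiring the triggering comparison to be significant as well still leaves 70%, 66% and 64%.

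**Boundaries that would fit inside 0.025.** O'Brien-Fleming with one half-way look: z = 2.250 at the end and 2.250 × √2 = 3.18 at the look, so p < 0.0015 then p < 0.0244. Haybittle-Peto: p < 0.001 then p < 0.0246 holds 0.025 per comparison with one look, but gives 0.0254 and 0.0257 with two and three.

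**The case against.** The strongest reply is that inflation has not been shown. The powered effect has a direction, and the same sentence also provides for stopping when there is no effect. If only a worse result on 80 mg triggers and the no-effect stop is binding, error stays below 5%. That stands for those rules. But nothing makes the no-effect stop binding, and if it means that both |d| are at most 0.2, error is 5.2 to 6.2% across 20 and 35 per group and triggers of 0.75 and 0.9. Nor does this reply help power, which falls equally with or without direction and the no-effect stop.

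Second, the simulation uses t-tests rather than the mixed model of V.A. True; the figures are illustrations, though the t-test is the basis of the plan's own power claim.

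Third, the number of looks is assumed. Accrual time is not stated, and if the trial finished within a year there would be no yearly look. The wording may also be carried over from a longer study: it speaks of studies in the plural, II.B has "independent of statin therapy over the 1 year dose-response", and II.E.a.iii says "blood will be collect over the 12 month intervention". The meaning of shortening is therefore open. The provision nevertheless stands in two sections of the current protocol and authorises action.

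Finally, a reader might infer from IV.A that the PIs are unblinded after a year and then conduct effort-dependent treadmill tests knowing the allocation. The documents do not support that. The sentence is broken by a removed name and can equally mean the biostatistician alone; the next sentence gives one person's examination of effects as a purpose; and study staff stay blinded. II.J lists the PI and the coordinator for conducting tests, but nothing says the PI would run them after unblinding. This is a matter for clarification only and adds nothing to the severity.

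**Conclusion.** The point holds as a missing rule: the overall 0.05 and the 80% power in II.C are not ensured while II.K.b and IV.E stand as written. Under the stated assumptions, error ranges from about 4% to about 8% and power from 81% down to 39%, depending entirely on how the review is conducted.

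A reader might infer that the trial's error rate is inflated, or that it reaches 8 to 12% (7.9, 10.3 and 12.3% with one, two and three looks) because significance at 0.025 would be tested at each one. The documents do not support either inference: no significance-based stop is written, and some rules consistent with the text hold 5%. The power loss is the more robust risk under an either-comparison trigger, but it too disappears if both comparisons must be large and significant. This should be fixed; it is not a demonstrated error in the result.

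**What to change.** In II.K.b and IV.E, delete shortening for a large effect and keep the DSMB safety and enrolment reviews.

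Alternatively, first reconcile the completer targets (60 in II.B, 105 in II.C). Then name week-12 VO2peak as the outcome and pre-specify one interim look, for example half-way (53 of 105 or 30 of 60 completers), with a boundary inside each 0.025: O'Brien-Fleming p < 0.0015 then p < 0.0244, or Haybittle-Peto p < 0.001 then p < 0.0246. These levels are for one look only; more looks need a recomputed final level. State whether both comparisons must cross. If one crossing stops the trial, power for placebo versus 80 mg falls from 80% to 72–73%. If both must cross, the loss is at most about 0.2 points.

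Any no-effect stop should be non-binding with a stated threshold, and the meaning of shortening should be spelled out. All this must be settled before by-arm data are reviewed.

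As a separate clarification, reword IV.A so that, apart from the safety unblinding already provided for, only the unblinded statistician and the DSMB see by-arm results before database lock, and make it agree with the blinding statements in II.B and II.E.a.xiii.

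The cost is protocol wording, plus either the informal early stop or the small power loss above. The statistician and DSMB are already in place.

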- i. Changes in Cardiorespiratory fitness (VO₂peak): Subjects will be tested for VO₂peak at baseline and post training using a Bruce protocol on a treadmill as previously performed (13, 97). Relative (ml/kg-1/min-1) and absolute (L/min-1) VO₂peak and treadmill time to exhaustion will be used as determinants of fitness while additional measures of respiratory quotient (RQ) and heart rate at each stage of the GXT, and heart rate recovery and excess post oxygen consumption following the test will also be measured as determinants of exercise training adaptations. Blood CK levels will be assessed 30 minutes following the cessation of exercise and also 24 hour later. In addition, sub-maximal exercise (60% HRR) measures of heart rate, RQ, and O₂ consumption will also be determined during exercise training sessions occurring during the first week and the last week of training.

b. Secondary Objectives:

- i. Mitochondrial Responses in Skeletal Muscle: Multiple aspects of mitochondrial function (basal and ADP-stimulated respiratory kinetics under multiple substrate combinations, H₂O₂ production and emitting potential) will be assessed in duplicate on permeabilized fiber bundles from freshly obtained muscle biopsy samples as previously described (61-64). Fibers are then freeze dried for determination of citrate synthase activity (index of mitochondrial content). Frozen muscle tissue will also be analyzed for electron transport complex activity, content (Western blot using complex I through V antibody cocktail) and cellular redox state (GSH/GSSG, thioredoxinred/thioredoxinox) as previously described (63). Of the remaining approximate ≥ 90 mg of muscle biopsy tissue, a small portion (<5

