- x. **Exercise Testing:** Whole body steady state submaximal O_2 consumption will be determined during a standard 6 min treadmill test (2.5 mph) to determine VO_2 cost. Subjects will then complete a ramped treadmill test (Bruce protocol) to determine cardiorespiratory fitness (VO_2 peak) and peak heart rate as previously

described (13). We will also investigate post exercise oxygen consumption and heart rate at 60, 90, 120, and 300 seconds after cessation of the max test to determine if exercise recovery is impacted by statins. Blood will be sampled for measurement of CK 20-30 minutes following the maximal exercise to assess potential muscle damage. Exercise testing will be repeated at week 12.

- xi. Cardiovascular Function: These measures include both heart rate and stroke volume performed under both resting and sub-maximal exercise conditions (performed on separate days). Stroke volume will be estimated by finometer placed on finger (80). Cardiovascular function will be repeated at week 12.
- xii. Physical Activity Monitoring: Physical activity levels and sedentary time will be assessed by pedometers and accelerometers (BodyMedia Sensewear) (75, 76) for 5 day periods. Physical activity monitoring will be repeated at week 12.
- xiii. Statin Therapy Intervention: Once participants have successfully completed baseline testing, the participant will be randomly assigned to 1 of 3 groups (1:1:1 ratio). Statins will be prescribed as a placebo or at a dosage of 20 or 80 mg/day (atorvastatin; Lipitor) by the study physician at KUMC, [name], MD. Subjects and research team will be blinded to the type and dose of statin. Statins will be dispensed by the KUMC Investigational Pharmacy at regular intervals during the participant's enrollment in the study. The study physician will provide care for any problems associated with the statin treatment after un-blinding by the chair of the Data Safety Monitoring Board, [name]. All doses fall within the norms of recent recommendations and are given chronically (2)

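### The analysis section's time levels do not match the VO2peak visits: week 12 is not listed, and with baseline only as a covariate the treatment-by-time test has 0 degrees of freedom

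*Combined protocol and SAP*

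**What the plan says.** Section V.A (Statistical and Data Analysis) describes a two-factor analysis, treatment group by "time of data collection (0, 1, 6, and 12 months) (within subject"), and names cardiorespiratory fitness as the primary outcome to which it applies. It then sets four rules:

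- Baseline: "For each measure, its baseline measure and age will be added as covariates to adjust for the individual difference at baseline".
- Test: "Two-way interaction between treatment and time will be added in the model for testing if the outcome changes differently between groups over time".
- Follow-on step: "If the test of trend difference is significant, then the comparison at each time point will also be considered", the purpose being "to identify when the difference between groups reaches the maximum".
- Estimates: "Least Square Means will be used for the aforementioned comparisons".

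The visit schedule is different. The primary objective (II.A.a) has VO2peak tested "at baseline and post training using a Bruce protocol on a treadmill". The procedures (II.E.a.x) add one repeat: "Exercise testing will be repeated at week 12". Section II.B gives a 12-week training and treatment period. Section II.C powers the trial on two VO2peak comparisons at 12 weeks, placebo versus 80 mg and 20 mg versus 80 mg, each two-sided at 0.025.

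Month-based wording also survives elsewhere: a one-year dose-response in II.B, 6- and 12-month enzyme tests and a 12-month blood volume in II.E.a.iii, and strength testing at 1, 6 and 12 months in II.E.a.vii.

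**The concern.** The analysis section should tell the analyst which test decides the primary question. Here it names a treatment-by-time interaction over visits that VO2peak does not have, and it leaves out the visit on which the sample size rests. It also does not say whether the baseline value is a covariate, a response, or both.

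This looks like more than one mistyped list. The follow-on step looks for the time at which the group difference peaks, and one follow-up visit cannot answer that.

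At stake is prespecification of the primary test. Someone has to choose among the possible models. Section IV.A plans to un-blind the principal investigators and the biostatistician after one year, and sections II.K and IV.E plan yearly data reviews that may shorten the study. The choice should be written down before then.

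**Working it through.** **Step 1: which visit the design rests on.** II.C gives 35 per group, standardized effect 0.75, two-sided alpha 0.025 and 80% power for a two-sample t-test. Solving for n gives 35.08 per group, and power at n = 35 is 79.9%, so the figure reproduces. It is a two-group comparison at one time point, week 12. The implied SD is 1.53 / 0.75 = 2.04 ml/kg/min.

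**Step 2: match the levels to the data.**

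| Level | In V.A's list | VO2peak measured |
|---|---|---|
| Baseline (0) | yes | yes |
| Week 12 | no | yes |
| Month 1 | yes | no |
| Month 6 | yes | no |
| Month 12 | yes | no |

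**Step 3: degrees of freedom of the interaction.** With 3 groups and T response times, df = (3 − 1)(T − 1).

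| Response times | T | df |
|---|---|---|
| 0, 1, 6, 12 months (list as written) | 4 | 6 |
| 1, 6, 12 months (list, baseline as covariate) | 3 | 4 |
| Baseline and week 12 | 2 | 2 |
| Week 12 only (baseline as covariate) | 1 | 0 |

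Comparing design-matrix ranks, with baseline and age included, gives the same four values. The last two rows are the only ones for which VO2peak has data. In the last row neither the interaction nor the step conditional on it can be computed, and the remaining group test is the treatment effect in a week-12 ANCOVA.

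**Step 4: if month 0 is kept as a response (conditional note).** Assume a random intercept and a common residual variance; the plan names no covariance structure. Let s be the SD of change and r the correlation of baseline with change, which the documents do not give. Baseline enters both rows with the same slope, so:

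- The difference of the two rows has residual variance s².
- Their sum has residual variance s²(1 − r²). This is no larger than that of the difference, so the random-intercept variance is estimated at 0.
- The pooled residual variance per row is [s² + s²(1 − r²)] / 4 = s²(1 − r²/2) / 2.
- The true residual variance of the week-12 row is s²(1 − 0.75r²), and that of the change is s².

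The ratio of model SE to true SE is therefore √(1 − r²/2) for the interaction contrast and √[(1 − r²/2) / (2(1 − 0.75r²))] for the week-12 least-squares-mean contrast. Type I error at nominal 0.025 is 2Φ(−2.241 × ratio).

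| r (assumed) | Interaction: ratio | Interaction: error | Week-12 mean: ratio | Week-12 mean: error |
|---|---|---|---|---|
| 0 | 1.000 | 0.0250 | 0.707 | 0.113 |
| −0.3 | 0.977 | 0.0285 | 0.716 | 0.109 |
| −0.5 | 0.935 | 0.0360 | 0.734 | 0.100 |
| −0.7 | 0.869 | 0.0515 | 0.773 | 0.083 |

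The last column ignores V.A's rule that time-point comparisons follow only after a significant interaction.

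**Step 5: the replacement loses no power.** For ANCOVA the residual SD is 2.04√(1 − r²). With 35 per group, a difference of 1.53, two-sided alpha 0.025 and 100 df, the noncentral t gives power of 0.804 / 0.843 / 0.909 / 0.982 for the same four values of r.

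**The case against.** The strongest reply is that the plan is closer to complete than V.A alone suggests. II.C already names both comparisons, the 12-week time point and 0.025 for each. Read with V.A's baseline and age covariates, that is nearly a week-12 ANCOVA. V.A is also general text for all outcomes. Biopsies are repeated at weeks 4 and 12 (II.E.a.iv), and for those a treatment-by-time test with baseline as a covariate works, with (3 − 1)(2 − 1) = 2 df. All of this stands, and it is why the remedy is short. It does not remove the conflict: V.A names cardiorespiratory fitness as the outcome to be analysed this way, does not carry over II.C's contrasts or alpha, and puts time-point comparisons behind a trend test.

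Two stronger readings are tempting, and the documents support neither.

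- A reader might infer that the model cannot be run at all. Using baseline twice does not stop it. If month 0 is kept and week 12 replaces the listed months, the interaction has 2 df. The failure belongs to the visit list and to the covariate-only reading.
- A reader might take 0.08 to 0.11 as the trial's type I error. Those values belong to the follow-on contrast, not to the interaction that V.A names as its test, and they rest on an assumed reading, covariance and correlation. For the interaction contrast the error stays near 0.025 at r = 0 and −0.3. If all arms are equal, the conditional step limits false follow-on claims to its own size: taken at 0.05, this is 0.05^(1 − r²/2) = 0.050 / 0.057 / 0.073 / 0.104. It gives no such protection if the two doses act alike and both differ from placebo. Under the pattern II.C expects, with 20 mg similar to placebo and 80 mg lower, neither II.C comparison is null. An analyst might also notice the zero random-intercept variance.

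**Conclusion.** The point holds as a mismatch within the current text. V.A's time levels give VO2peak data only at month 0 and omit week 12, the one follow-up visit and the powered one. The role of baseline is left open between two readings. With baseline only as a covariate, the named test and its conditional step have 0 df against the 4 that the listed post-baseline months imply, and an adjusted week-12 comparison is what remains. With month 0 as a response, the test has 2 df and baseline is on both sides of the model.

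These conclusions need no assumption beyond the visit schedule. The error rates in the working do need assumptions, and they are not established properties of the plan. The case for correction rests on a stated primary test that does not fit its endpoint, not on a demonstrated inflation. The same problem affects any other outcome with only baseline and week 12, such as insulin sensitivity from the IVGTT.

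**What to change.** In V.A:

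1. State the primary analysis as ANCOVA of week-12 VO2peak on treatment, baseline VO2peak and age, with the two II.C contrasts (placebo versus 80 mg; 20 mg versus 80 mg), each two-sided at 0.025.
2. Say that the trend-test condition does not apply to these contrasts, because it cannot be computed with one follow-up visit.
3. Use the same form for other outcomes measured only at baseline and week 12. For outcomes also measured at week 4, use weeks 4 and 12 as responses with baseline only as a covariate, and name the covariance structure.
4. Replace the month list with the actual visits for each outcome.

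Elsewhere, reconcile the month-based wording in II.B, II.E.a.iii and II.E.a.vii with the 12-week design.

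The cost is wording only: no new visits, data or participants. Baseline and age adjustment and the 0.025 level are already in the plan. The change should be made before the un-blinding planned in IV.A.
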